4.2. Medical History

Medical history will include the following:

- COVID-19 with start date as the date of onset of first symptom related to COVID-19
- Risk factors for severe COVID-19/hospitalization due to COVID-19 as defined below
- Whether the patient is receiving oxygen at home by nasal cannula

CONFIDENTIAL

Page 20 of 61

VV-RIM-00147241-1.0 Approved - 12 Mar 2021 GMT-5:00

• Pregnancy or breastfeeding status, if applicable

Risk factors for severe COVID-19 are defined as follows:

- a. Age \geq 50 years (cohort 1 only)
- b. Obesity, defined as: BMI ≥30 kg/m² (cohort 1 only) BMI (kg/m2) ≥95th percentile for age and sex based on CDC growth charts (cohort 2 ≥2 years only)
- c. Cardiovascular disease, including hypertension
- d. Chronic lung disease, including asthma
- e. Type 1 or type 2 diabetes mellitus
- f. Chronic kidney disease, including those on dialysis
- g. Chronic liver disease
- h. Pregnancy
- i. Immunosuppressed, based on investigator's assessment Examples include cancer treatment, bone marrow or organ transplantation, immune deficiencies, HIV (if poorly controlled or evidence of AIDS), sickle cell anemia, thalassemia, and prolonged use of immune-weakening medications
- j. Any underlying genetic condition, neurologic condition, metabolic condition, or congenital heart disease deemed by the investigator to be a risk factor for severe COVID-19 (cohort 2 only)

4.3. **Prior / Concomitant Medications or Procedures**

Medications/Procedures will be recorded from the day of informed consent until the final study assessment (Day 169 or early study discontinuation or death). Medications will be coded to the ATC level 2 (therapeutic main group) and ATC level 4 (chemical/therapeutic subgroup), according to WHO Drug Dictionary (WHODD) version 202003 or later. Patients will be counted once in all ATC categories linked to the medication.

Prior medications/procedures are: medications taken or procedures performed prior to administration of the study drug.

Concomitant medications/procedures are: medications taken or procedures performed following the first dose of study drug through the final study assessment (Day 169 or early study discontinuation or death). This includes medications taken that started before the study and are ongoing during the study.

Only select concomitant medications will be captured in this trial. The select list of medications include, but are not limited to, corticosteroids, remdesivir, lopinavir-ritonavir, chloroquine, hydroxychloroquine, interferon beta, and convalescent serum. In addition, any concomitant procedures used to treat an adverse event will be captured in this trial.

Analysis of medications data will be focused on the targeted medications (specified in the protocol) that are expected to be reviewed and recorded by sites.

CONFIDENTIAL

4.4. **Rescue Medication/or Prohibited Medication During Study**

Patients can receive rescue therapy for COVID-19 per local standard-of-care. Rescue treatments are not provided as part of the study.

Patients are not permitted to receive any medication specified in the exclusion criteria (of the protocol) for study enrollment, unless medically indicated. Patients may otherwise continue their normal regimen of medications and procedures. All data collected on medications/procedures (pre-treatment and concomitant) will be summarized.

4.5. Efficacy Endpoints

4.5.1. Primary Efficacy Endpoint

Cohort 1

The primary clinical efficacy endpoint for phase 3 is the proportion of patients with ≥ 1 COVID-19-related hospitalization or all-cause death through day 29.

4.5.2. Secondary Efficacy Endpoints

The secondary endpoints for phase 3 are:

Cohort 1

The key secondary endpoints for phase 3 are

- Proportion of patients with ≥1 COVID-19-related hospitalization or all-cause death from day 4 through day 29
- Time to COVID-19 symptoms resolution.

The other secondary efficacy endpoints for phase 3 are:

- Proportion of patients with ≥1 COVID-19-related hospitalization, emergency room (ER) visit, or all-cause death through day 29
- Proportion of patients with ≥1 COVID-19-related medically-attended visit or all-cause death through day 29
- Proportion of patients with COVID-19 related medically-attended visits by type of visit(s) (hospitalization, ER visit, urgent care, and/or physician's office/telemedicine visit) through day 29
- Proportion of patients with ≥2 COVID-19 related medically-attended visits through day 29
- Cumulative incidence of ≥1 COVID-19-related hospitalization or all-cause death through day 29
- Cumulative incidence of COVID-19-related hospitalizations or ER visits through day 29

- Cumulative incidence of patients with ≥1 COVID-19-related medically-attended visit or all-cause death through day 29
- Days of hospitalization due to COVID-19
- Proportion of patients admitted to an ICU due to COVID-19 by day 29
- Proportion of patients requiring supplemental oxygen due to COVID-19 by day 29
- Proportion of patients requiring mechanical ventilation due to COVID-19 by day 29
- Total number of COVID-19-related medically-attended visits through day 29
- Time to all-cause death
- All-cause death by day 29, day 120, and day 169
- Time-weighted average change from baseline in viral load (log₁₀ copies/mL) from day 1 to day 7, as measured by RT-qPCR in NP swab samples (patients enrolled prior to protocol amendment 6 only)
- Change from baseline in viral load at each visit, as measured by RT-qPCR in NP samples

Cohort 2

The secondary endpoints for phase 3 are:

- Proportion of patients with ≥1 COVID-19-related hospitalization or all-cause death through day 29
- Proportion of patients with ≥1 COVID-19-related hospitalization or all-cause death from day 4 through day 29
- Proportion of patients with ≥1 COVID-19-related hospitalization, ER visit, or all-cause death through day 29
- Proportion of patients with ≥1 COVID-19-related medically-attended visit or all-cause death through day 29
- Proportion of patients with ≥1 COVID-19-related medically-attended visit by type of visit(s) (hospitalization, ER visit, urgent care, and/or physician's office/telemedicine visit) through day 29
- Proportion of patients with ≥2 COVID-19-related medically-attended visits through day 29
- Cumulative incidence of patients with ≥1 COVID-19-related hospitalization or allcause death through day 29
- Cumulative incidence of patients with ≥1 COVID-19-related hospitalization, ER visit, or all-cause death through day 29
- Cumulative incidence of patients with ≥1 COVID-19-related medically-attended visit or all-cause death through day 29

- Days of hospitalization due to COVID-19
- Proportion of patients admitted to an ICU due to COVID-19 by day 29
- Proportion of patients requiring supplemental oxygen due to COVID-19 by day 29
- Proportion of patients requiring mechanical ventilation due to COVID-19 by day 29
- Total number of COVID-19-related medically-attended visits through day 29
- Time to all-cause death
- All-cause death by day 29, day 120, and day 169.
- Time-weighted average change from baseline in viral load (log₁₀ copies/mL) from day 1 to day 7, as measured by RT-qPCR in NP swab samples.
- Change from baseline in viral load at each visit, as measured by RT-qPCR in NP samples
- Immunogenicity, as measured by ADA and NAbs to REGN10933 and REGN10987

Cohort 3

The secondary endpoints for phase 3 are:

- Concentrations of REGN10933 and REGN10987 in serum over time
- Immunogenicity, as measured by anti-drug antibodies and neutralizing antibodies to REGN10933 and REGN10987

Endpoint definitions

Time to COVID-19 symptoms resolution will be defined as time from randomization to the first day during which the subject scored none on all symptoms except fatigue, headache, and cough, which can be mild/moderate or none. Patients with missing baseline assessment will not be included in the analysis.

Time-weighted average of change from baseline viral load in the nasopharyngeal (NP) swab samples from day 1 through day 7 will be calculated for each patient with intensive viral load data collection (ie, those randomized under protocol amendment 5 or earlier) using the linear trapezoidal rule as the area under the curve for change from baseline at each time point divided by the time interval for the observation period. Accompanying descriptive analyses will be provided at the individual timepoints used to calculate the TWA.

For example, the time-weighted average change from baseline in viral load in the nasopharyngeal (NP) swab samples till the last observation day t_k will be calculated using formula

$$TWA_{[0-k]} = \left[\sum_{i=1}^{k} (t_i - t_{i-1}) * (D_i + D_{i-1})/2\right] / (t_k - t_0)$$

Where

• k=11 refers to 11 post-baseline assessments

CONFIDENTIAL

Page 24 of 61

- D_i is the change from baseline in viral load value (log10 copies/mL) obtained at time t_i , $D_0 = 0$
- t_i is the time (day) for which D_i is measured, such as $t_0 = 1$ (day) for baseline and $\{t_i\} = 3, 5, 7, 9, 11, 13, 15, 18, 22, 25, 29$, for i=1 to 11 where the postbaseline assessment is taken.
- If the *D_i* is not available per protocol or missing due to failed test or other reasons, only the time points with non-missing values will be included into the calculation. For example, we will calculate the TWA till day 7. In this case, data is not available at day 1, 2, 4, and 6 per the protocol schedule of events. Suppose the scheduled assessment result is missing at day 5 due to a failed test but non-missing at day 3 and day 7, then

$$TWA_{[0-7]} = [(t_3 - t_0) * (D_3 + D_0)/2 + (t_7 - t_3) * (D_7 + D_3)/2]/(t_7 - t_0)$$

Baseline is defined as the last non-missing value prior to the study drug infusion. Patients with missing baseline will be excluded from the analysis of virologic endpoints. Virologic data after start of study drug infusion will be used as post-baseline assessments.

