/Endpoints	• For cohort 2, secondary endpoint analyses will be descriptive
	Virologic analyses for all cohorts will be secondary and descriptive
	• Cohort 1 will enroll up to 300 patients in an optional sub-study to assess, as an exploratory objective, the potential impact of REGN10933+REGN10987 on the endogenous immune response
Sample Size	• Enrollment in phase 3 cohort 1 is anticipated to be up to approximately 8500 patients
	• Cohort 2 will enroll up to approximately 180 patients; there will be a minimum enrollment of 20 patients <10 kg (10 per treatment group) and 20 patients between ≥10 kg and <40 kg (10 per treatment group)
	No minimum or maximum enrollment is planned for cohort 3
	• Cohort 2 and cohort 3 may continue to enroll after enrollment of cohort 1 has been completed

¹ Phase 3 adaptations were initially implemented in protocol amendment 6. Modifications to the phase 3 adaptations were subsequently implemented in response to health authority feedback (protocol amendment 7) and prior to phase 3 statistical analyses (protocol amendment 8). Refer to the amendment history table for more detailed information.

Virologic Efficacy

An interim analysis of pooled phase 1/2 data (n=275) was conducted to assess preliminary virologic and clinical efficacy of REGN10933+REGN10987. Among patients who were SARS-CoV-2 seronegative at baseline, those who received REGN10933+REGN10987 had a greater reduction in viral load through day 7 compared with those who received placebo, as measured by time-weighted average (TWA) change from baseline. For example, seronegative patients receiving either REGN10933+REGN10987 2400 mg or 8000 mg (combined analysis) had a TWA viral load change of -1.94 log₁₀ copies/ml, versus -1.37 log₁₀ copies/ml in the placebo arm (difference between combined dose group and placebo, -0.56 log₁₀ copies/mL; nominal p=0.0165). Post-hoc analysis of virologic outcomes by baseline viral load found that patients with the highest viral load at baseline had the largest treatment benefit.

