- Days of hospitalization due to COVID-19
- Proportion of patients admitted to an intensive care unit due to COVID-19 by day 29
- Proportion of patients requiring supplemental oxygen due to COVID-19 by day 29
- Proportion of patients requiring mechanical ventilation due to COVID-19 by day 29
- Total number of COVID-19-related medically-attended visits through day 29
- Time to all-cause death
- All-cause death by day 29, day 120, and day 169

Virologic

- Time-weighted average change from baseline in viral load (log₁₀ copies/mL) from day 1 to day 7, as measured by RT-qPCR in nasopharyngeal swab samples
- Change from baseline in viral load at each visit, as measured by RT-qPCR in nasopharyngeal swab samples

ADA

• Immunogenicity, as measured by anti-drug antibodies and neutralizing antibodies to REGN10933 and REGN10987

Cohort 3

The secondary endpoints for phase 3 are:

PK/ADA

- Concentrations of REGN10933 and REGN10987 in serum over time
- Immunogenicity, as measured by anti-drug antibodies and neutralizing antibodies to REGN10933 and REGN10987

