Patients enrolled in cohort 2 will follow the schedule events in Table 8. These patients will also have NP swabs and blood samples collected approximately every week through day 29, with an NP swab additionally collected on day 3. To reduce overall patient burden of blood sampling in this younger cohort, the frequency of blood sample collection and the total amount of blood collected per visit will vary according to body weight. In addition, patients in this cohort will be randomly assigned to one of four staggered PK-ADA sampling schedules. This will be done according to a central randomization scheme using an interactive web response system (IWRS).

Patients enrolled in cohort 3 who are ≥18 years of age will follow the schedule of events in Table 7; those <18 will follow the schedule of events in Table 8.

After the final in-person visit, all cohorts will have 2 follow-up phone calls to collect safety information, including (when applicable) additional information regarding pregnancy outcome (Section 9.2.5).

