limited to patients who were randomized prior to protocol amendment 6. A similar analysis will be performed for mFAS with baseline serostatus as an additional term to the ANCOVA model. The least squares means estimates for the time-weighted average mean change from baseline in viral load for each treatment group, as well as the difference comparing each anti-spike mAb treatment arm versus placebo, will be presented along with the corresponding p-value, standard error, and associated 95% confidence interval. Subgroup analysis of the TWA change from baseline in viral load at each visit will also be performed by baseline viral load categories (>10⁴ copies/mL, >10⁵ copies/mL, >10⁶ copies/mL, >10⁷ copies/mL).

For phase 2, time to negative RT-PCR results through day 15 for seronegative mFAS will be analyzed using the stratified log-rank test with randomization strata as a stratification factor. Estimates of median times and associated 95% confidence intervals using the Kaplan-Meier method will be reported. The hazard ratio and its 95% CI for time to negative RT-PCR results through day 15 will be estimated by the Cox regression model with terms for treatment group, baseline viral load, treatment by baseline interaction, randomization strata. P-value from the stratified log-rank test for time to negative RT-PCR results through day 15 will be reported. Similar analysis will be performed for the mFAS with baseline serostatus as an additional term to the model.

Proportion endpoints based on observed virologic data will be compared between groups using similar method as the proportion clinical endpoints. The analyses will be performed for seronegative mFAS as well as for mFAS.

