Starting with protocol amendment 8, cohort 1 will be randomized 1:1 to a single dose of REGN10933+REGN10987 1200 mg IV or REGN10933+REGN10987 2400 mg IV and randomization stratified by country. Patients in this cohort will no longer be randomized to placebo.

Cohort 2

Starting with Protocol Amendment 6, pediatric patients were enrolled into cohort 2, randomized in a 1:1:1 allocation ratio to a single IV dose of REGN10933+REGN10987 at a lower dose level, at a higher dose level, or to placebo, where the exact dose was tiered according to body weight to match REGN10933+REGN10987 2400 mg or REGN10933+REGN10987 1200 mg, as defined in Table 1.

Starting with protocol amendment 8, cohort 2 will be randomized 1:1 to a single IV dose of REGN10933+REGN10987 high dose or REGN10933+REGN10987 low dose, as defined in Table 1. Patients in this cohort will no longer be randomized to placebo.

		1
Body Weight Group	Dose Equivalent for REGN10933+REGN10987 1200 mg IV Dose (600 mg per mAb)	Dose Equivalent for REGN10933+REGN10987 2400 mg IV Dose (1200 mg per mAb)
≥40 kg	1200 mg (600 mg per mAb)	2400 mg (1200 mg per mAb)
\geq 20 kg to <40 kg	450 mg (225 mg per mAb)	900 mg (450 mg per mAb)
\geq 10 kg to <20 kg	224 mg (112 mg per mAb)	450 mg (225 mg per mAb)
\geq 5 kg to <10 kg	120 mg (60 mg per mAb)	240 mg (120 mg per mAb)
\geq 2.5 kg to <5 kg	60 mg (30 mg per mAb)	120 mg (60 mg per mAb)
<2.5 kg	30 mg (15 mg per mAb)	60 mg (30 mg per mAb)

Table 1:REGN10933+REGN10987 IV Doses for Each Weight Group, Phase 3 Cohort
2 (Ages 0 to <18 Years)	In phase 3 cohort 2, randomization will be stratified by country

Cohort 3

Patients in cohort 3 will be randomized in a 1:1 allocation ratio to co-administered REGN10933+REGN10987 combination therapy IV single dose (no placebo). Patients in cohort 3 who are \geq 18 years of age will follow the REGN10933+REGN10987 dose levels described for cohort 1 (1200 mg and 2400 mg). Patients in cohort 3 who are <18 years of age will follow the adjusted REGN10933+REGN10987 dose levels described in Table 1.

In phase 3, cohort 3, randomization will not be stratified.

The study design schematic before protocol amendment 8 is presented in Figure 1 and Figure 2.

CONFIDENTIAL

Page 14 of 61

Figure 2: Study Flow Diagram, Phase 3 (Cohort 2 Patients; Cohort 3 Patients <18 Years)

2.2. Sample Size and Power Considerations for Phase 3

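### The SAP's definition of time-weighted average viral load carries an over-broad Amendment 5 condition that, read literally, shuts cohort 2 out of one of its listed secondary endpoints

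*SAP*

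**What the plan says.** **The endpoint lists.** SAP section 4.5.2 lists this measure for cohort 2: "Time-weighted average change from baseline in viral load (log₁₀ copies/mL) from day 1 to day 7, as measured by RT-qPCR in NP swab samples". The cohort 2 bullet has no condition on amendment. The cohort 1 bullet for the same measure ends with a limit to patients enrolled before Amendment 6. Protocol section 4.2 follows the same pattern: the cohort 1 bullet is limited, and the cohort 2 bullet ("from day 1 to day 7, as measured by RT-qPCR in nasopharyngeal swab samples") is not.

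**The definition.** After the lists for all three cohorts, SAP section 4.5.2 has a block of endpoint definitions. There the TWA "will be calculated for each patient with intensive viral load data collection (ie, those randomized under protocol amendment 5 or earlier". The sentence names no cohort. It is followed by a trapezoidal formula, an 11-visit schedule and a rule for missing time points.

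**When cohort 2 began.** SAP section 2.1: "Starting with Protocol Amendment 6, pediatric patients were enrolled into cohort 2, randomized in a 1:1:1 allocation ratio". The footnote to Table 1 in protocol section 3.2.1.5 agrees: "Phase 3 adaptations were initially implemented in protocol amendment 6".

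**The analysis sections.** Protocol section 11.4.3.2 says that, in cohort 1, the TWA analysis is "limited to patients who were randomized prior to protocol amendment 6". It sets no such limit for cohort 2. SAP section 5.7.2 repeats the limit under its cohort 1 heading. For cohort 2 it says only that virologic data are summarised descriptively.

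**The swabs.** Protocol section 6.1.3 gives cohort 2 roughly weekly swabs to day 29, with an "NP swab additionally collected on day 3".

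**Departures.** SAP section 1.2.4 states that nothing was changed from the statistical section of protocol amendment 8.

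**The concern.** A programmer who derives TWA from this SAP has one definition to work from. It selects patients by the amendment under which they were randomised, and no child in cohort 2 was randomised under an amendment that qualifies. The result would be either an empty table for a listed paediatric endpoint or a derivation that departs from the written definition without saying so.

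What is at stake is one derived summary. TWA is the listed cohort 2 measure that combines the extra day 3 swab with day 7 into a single value per child. Protocol section 3.2.1.5 reports that in phase 2 the treated and placebo groups could be told apart from 2 days after treatment, so the measure covers the period of interest.

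**Working it through.** No power, sample size or alpha figure is involved, and the plan gives no figure of its own to reproduce. The check has three steps.

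**1. Who satisfies the definition.**
- Condition in the SAP definition: randomised under Amendment 5 or earlier.
- Cohort 2 enrolment: from Amendment 6 (SAP section 2.1).
- Planned cohort 2 size: up to about 180 (SAP section 2.2).

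The two sets do not overlap, so 0 of up to about 180 qualify.

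**2. Where the condition belongs.**

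| Place | Cohort 1 | Cohort 2 |
|---|---|---|
| Protocol 4.2, endpoint list | limited to before Amendment 6 | no limit |
| Protocol 11.4.3.2, analysis | limited to before Amendment 6 | no limit |
| SAP 4.5.2, endpoint list | limited to before Amendment 6 | no limit |
| SAP 5.7.2, analysis | limited to before Amendment 6 | descriptive, no limit |
| SAP 4.5.2, definition | limited | limited, because no cohort is named |

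Only the last row applies the limit to cohort 2. That row also conflicts with the statement in SAP section 1.2.4.

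**3. Whether a cohort 2 value can be computed.** The SAP formula is TWA = [Σ (tᵢ − tᵢ₋₁)(Dᵢ + Dᵢ₋₁)/2] / (t_k − t₀), with D the change from baseline in log₁₀ copies/mL, D = 0 at baseline and t₀ = day 1. In the lines below, D3 means the change at day 3, and so on.

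- Schedule before Amendment 6 (days 1, 3, 5, 7): [2·D3/2 + 2(D3 + D5)/2 + 2(D5 + D7)/2]/6 = D3/3 + D5/3 + D7/6.
- Cohort 2 (days 1, 3, 7): [2·D3/2 + 4(D3 + D7)/2]/6 = D3/2 + D7/3.
- Cohort 1 from Amendment 6 (days 1, 7): [6·D7/2]/6 = D7/2.
- Cohort 2 child with day 3 only: [2·D3/2]/2 = D3/2, averaged over days 1 to 3.

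The limit makes sense in cohort 1 from Amendment 6, where TWA is no more than half the day 7 change. It has no such basis in cohort 2. The SAP's own worked example, with day 5 missing and days 3 and 7 present, is the cohort 2 pattern. Its missing-point rule also covers time points that the schedule does not include.

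The weights show why a minimum-data rule is needed. They sum to 1/2 + 1/3 = 5/6 when days 3 and 7 are both present, but to 1/2 with day 7 alone. A change of size D already reached by day 3 and held to day 7 is recorded as 5D/6 in one child and D/2 in another. A child with day 3 only has no day 1 to day 7 average at all.

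**The case against.** The strongest reply is that the intended rule can be recovered. The definition does not use the word only. Where the SAP does use it, the text concerns cohort 1. The cohort 2 bullet omits the limit, the protocol ties it to cohort 1, and the SAP says that it follows the protocol. Read together, these give a limit in cohort 1 and none in cohort 2. This stands, and it makes the fault one of drafting. It does not remove the fault: a definition should not have to be overridden by inference from other sections, and the descriptive-summary sentence in SAP section 5.7.2 supplies no TWA rule.

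A second reply also stands. The next bullet in the cohort 2 list is change from baseline at each visit, and SAP Table 7 has a day 3 row for these patients. The day 3 and day 7 results are therefore reported whichever way the definition is read. What could be lost is a combination of two values already shown.

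Third, no inference depends on it. The cohort 2 primary endpoints are safety and drug concentrations. Its analysis is descriptive with no multiplicity adjustment, and it lies outside the ten-step hierarchy. Placebo randomisation stopped on 25 February 2021, so later children have no concurrent placebo group.

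A reader might infer that the sponsor removed TWA for children, or that early virologic information on them will be missing. The documents support neither. Both lists keep the endpoint, the swabs are scheduled, and the by-visit analysis uses them.

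**Conclusion.** The point holds as a contradiction within the SAP, and between the SAP and the protocol, with limited consequence. Read literally, the definition leaves a listed cohort 2 secondary endpoint with 0 patients out of up to about 180 planned. No confirmatory result, error rate or cohort 1 analysis is touched.

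This rests on three assumptions. First, no child was randomised into cohort 2 before Amendment 6, as SAP section 2.1 says. Second, 180 is a planned maximum; the documents do not give the number of children with usable swabs, and a missing baseline excludes a child in any case. Third, the protocol in hand is Amendment 10 US while the SAP follows Amendment 8. The amendment history for 9 US and 10 US lists no change to the cohort 2 TWA endpoint or to the cohort 1 limit, so the Amendment 8 text is taken to be the same on this point.

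**What to change.** In the endpoint definitions of SAP section 4.5.2:

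1. Attach the Amendment 5 condition to cohort 1 only.
2. State that in cohort 2 the TWA from day 1 to day 7 uses the baseline, day 3 and day 7 swabs with the existing trapezoidal formula (D3/2 + D7/3 when all are present), summarised descriptively by treatment group.
3. Require a day 7 value, so that a child with only a day 3 swab is not reported as a day 1 to day 7 average. Report in each group how many values rest on day 7 alone.
4. Note that the schedule with k = 11 in that section is the one used before Amendment 6.
5. State that cohort 2 values are not pooled with values from before Amendment 6, since they rest on two post-baseline swabs in the window where the earlier schedule had three.

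The cost is a few sentences in the SAP and an entry in its revision history. No new visits, samples or alpha are needed. Children without a day 7 swab drop out of the TWA summary but still count at day 3 in the by-visit summary.
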